5. PLANNED ANALYSES

There is no formal interim analysis planned for this study. However, the accrued data from any cohort may be analyzed for internal decision-making purposes.

A final analysis is planned for this study which will be performed at the end of study (defined as 18 months after the last patient has been enrolled in the study or all patients have discontinued the study treatment, whichever comes earlier in the protocol amendment 5) and after database lock.

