- If the imputed death date is prior to the last known alive date, then the death date

will be imputed as last known alive date+1.

If death date is totally missing, dates will be imputed as the last known alive date +
 1.

Note: if the imputed death date is after cut-off date, then the death date will be imputed as cut-off date.

Last known alive date

- If year and month are known but the day is unknown, day will be imputed as 1st.
- If only year is known, month and day would be imputed as Jan 1st.

Last dose date

Missing or partial date of last dose date of study treatment:

- If the date is partially missing, then impute the date as the last day of given part of
 original last dose date. If the day is missing, imputed date will be the last day of the
 month of the partial last dose. If the month is missing, imputed date will be the last
 day of the year of the partial last dose. If the imputed date is after the date of death
 (if the subject died) / last known alive date (if the subject is not known to die) / EOT
 date / EOS date, then it will be replaced with the earliest of the above.
- If the date is completely missing, then impute the earliest of the above.

Subsequent anti-cancer therapy

Missing or partial start date of anti-cancer therapy after end of study treatment:

- If the date has no missing year and month but the day is missing. And if the date has same year and month as last dose date, then equal to last dose date+1, else 15th day of the month will be used.
- If the date has no missing year, but has missing month, and the year of last dose date
 is the same as the year of the start date, the date of last dose+1 will be used.
- If the date has no missing year, but has missing month, and the year of last dose is before the year of the start date, then July 1st will be used.
- If the start date is completely unknown, then use the date of last dose+1.

Oncology Diagnosis History Dates

- If year is missing, do not impute.
- if year and month are known but the day is unknown, day will be imputed as 15.
- If only year is known, month and day would be imputed as July 1st.

Note: The imputed date will be compared to inform consent date. If it is later than the inform consent date, the incomplete date will be imputed as the inform consent date.

Date of Progression/ Date of Last Tumor Assessment

- If year and month are known but the day is unknown, day will be imputed as 1st.

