16.5. PROGRESSIVE-FREE SURVIVAL (PFS)

PFS is defined as the time (in months) from the date of first study medication to the earliest date of disease progression or death of any cause, whichever occurs first.

Protocol Number: 2018-689-00US1 Page 32 of 43

Progression-free survival (PFS) (months) = (<date of progression or death or censoring > - <date of first dose of study medication> + 1)/30.4375.

A patient is deemed to be censored, according to the rules specified in Table 4 below:

Table 2 Progression-Free Survival Censoring Rule

-	Τ	D (CD :		E 4/6
#	Situation	Date of Progression	Outcome	Event/Censor reason
		or Censoring		
1	Death (without previously	Date of death	Event	Death
	documented progressive disease			
	[PD]) within two evaluable			
	tumor assessments[a] from last			
	evaluable tumor assessment or			
	first dose (if no post-baseline			
	tumor assessment)			
2	Death (without previously	Date of last evaluable	Censored	Death after two or more
	documented PD) after two or	tumor assessment or		consecutive missed or
	more consecutive missed/non-	date of first dose (if no		NE tumor assessments
	evaluable tumor assessments[a]	post-baseline tumor		
	from last evaluable tumor	assessment)		
	assessment or first dose (if no			
	post-baseline tumor assessment)			
3	Progression within two	Date of progression	Event	Disease Progression
	evaluable tumor assessments[a]			
	from last evaluable tumor			
	assessment or first dose (if no			
	post-baseline tumor assessment			
 	before PD)	D . Cl . 1 11		
4	Progression after two or more	Date of last evaluable	Censored	Progression after two or
	consecutive missed/non-	tumor assessment or		more consecutive
	evaluable tumor assessments ^[a]	date of first dose (if no		missed or NE tumor
	from last evaluable tumor	post-baseline tumor		assessments
	assessment or first dose (if no	assessment before PD)		
	post-baseline tumor assessment			
5	before PD)	Date of last evaluable	Censored	Deagrassian - A
3	Progression after new anti-		Censorea	Progression after new
	cancer treatment	tumor assessment before new anti-cancer		anti-cancer therapy
		treatment or date of		
		first dose (if no post-		
		baseline tumor		
		assessment before new		
		anti-cancer)		
6	No baseline tumor evaluable	Date of first dose	Censored	No baseline assessment
١	assessment and alive	Date of first dose	Censored	No baseine assessment
1	LASSESSIFICITE ALICE ALIVE		- 1	27 (1 1)
7		Date of first dose	Cencored	No noct-baceline

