- From Day 162 (week 24) onwards (when the scheduling changes to 12-weekly assessments), two missing consecutive assessments equates to 182 days (2*12 weeks + 7 days for an early assessment + 7 days for a late assessment) since last evaluable tumor assessment.

[b] for patients who receive new anti-cancer therapy, the following rules will apply:

If the start date of new anti-cancer therapy is partial or missing, the imputation rules refer to section 7.10.

If an assessment occurs on the same day as the start of new anti-cancer therapy, the assessment will be used as it will be assumed the assessment occurred prior to the administration of new anti-cancer therapy).

The median and quartiles for PFS and the PFS rates at 6 months, 12 months, together with their two-sided 95% confidence intervals will be estimated for each dose level (Stage 1) and malignancy type (Stage2) using the Kaplan-Meier method. The 95% CI for the median will be calculated from a log-log transformation based on the method by Brookmeyer and Crowley (1982).

Kaplan-Meier curves will be plotted. In case the number of responses in each group is very small, PFS may be listed only.

PFS follow-up time will be summarized by reversed Kaplan-Meier method (i.e. using different censoring rule which reverses censoring indicator of PFS, i.e. patients who progressed or died in PFS analysis will be censored at the date of progression or death, patients who are censored in PFS analysis will be assigned indicator of "event" with the same duration for PFS) to calculate median, first and third quartiles and 95% CIs.

Frequency and percentage for each type of event (PD or death) and censoring reasons will be presented as categories.

The PFS time or censoring time and the reasons for censoring will also be presented in a patient listing for FAS.

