17.2. ADVERSE EVENTS

Treatment-emergent adverse events (TEAEs) are defined as AEs with onset date on or after the first dose of study medication and no later than 30 days after the date of last study treatment administration or start of a new treatment of anti-neoplasm therapy, whichever is earlier. An exception is that study medication related SAE collected later than 30 days after the last treatment date or start of a new treatment of anti-neoplasm therapy will be treated as TEAEs.

Refer to Section 7.10 for handling of partial dates for AEs. In the case where it is not possible to classify an AE as treatment-emergent or not, the AE will be classified as treatment-emergent.

All AEs will be listed, and only TEAE will be summarized.

The missing severity will be classified as grade 3. Relationship, as indicated by the Investigator, is classified as "Not related", "Related". TEAEs with a missing relationship to study medication will be regarded as "related" to study medication.

Protocol Number: 2018-689-00US1 Page 37 of 43

TEAE OVERVIEW

An overall summary of TEAEs will include the number of patients with:

- Any TEAE
- Any TEAEs by maximum CTCAE grade
- Any TEAE of CTCAE Grade 3 or higher
- Any TEAE Leading to Dose Modification
 - Any TEAE Leading to Dose Reduction
 - o Any TEAE Leading to Drug Interruption
- Any TEAE Leading to Drug Discontinuation
- Any TEAE Leading to Death
- Any Treatment Related TEAE
- Any Treatment Related TEAE of CTCAE Grade 3 or higher
- Any Treatment Related TEAE Leading to Dose Modification
 - Any Treatment Related TEAE Leading to Dose Reduction
 - Any Treatment Related TEAE Leading to Drug Interruption
- Any Treatment Related TEAE Leading to Drug Discontinuation
- Any Treatment Related TEAE Leading to Death
- Any Serious TEAE
- Any Treatment Related Serious TEAE
- Any Special Interest TEAE (AESI)
- Any Treatment Related AESI

TEAE SUMMARY

All TEAE will be summarized (the number and percent of patients) by SOC, PT and maximum CTCAE grade (All Grade, Grade ≥3, Grade 1/2).

The following categories will be summarized (the number and percent of patients) by PT and maximum CTCAE grade (All Grade, Grade ≥3, Grade 1/2).

	Summary scope
	- Any TEAE
	- TEAEs with CTCAE grade 3 or higher (maximum CTCAE
	grade by Grade 5, Grade 4, Grade 3)
TEAE	- TEAEs leading to dose modification
TEAE	 TEAEs leading to dose interruption
	 TEAEs leading to dose reduction
	- TEAEs leading to discontinuation of study drug

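### Incomplete start dates of subsequent anti-cancer therapy are imputed with no check against documented progression, so a true PFS event can be censored; in three of the five branches the post-dose TEAE tail also falls to about one day

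*SAP*

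**What the plan says.** SAP 7.10 has five branches for a partial or missing start of subsequent therapy:

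1. Day missing, same month as last dose: last dose + 1 ("And if the date has same year and month as last dose date, then equal to last dose date+1, else 15th day").
2. Day missing, another month: "else 15th day of the month will be used".
3. Month missing, same year as last dose: last dose + 1 (if the year of last dose "is the same as the year of the start date, the date of last dose+1 will be used").
4. Month missing, later year: 1 July.
5. Date fully missing: last dose + 1.

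This block has no comparison with progression, death or the last scan. Elsewhere in 7.10 imputed dates are checked: death against last known alive, last dose against death and end of treatment, diagnosis against consent.

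The PFS section takes the imputed date over directly: "If the start date of new anti-cancer therapy is partial or missing, the imputation rules refer to section 7.10". Row 5 of SAP Table 2 (its label begins "Progression after new anti") censors such a progression at the last evaluable assessment before the new therapy. An assessment on the day the therapy starts is still used.

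The same date limits the safety windows. SAP 17.2 counts AEs with onset "no later than 30 days after the date of last study treatment administration or start of a new treatment of anti-neoplasm therapy", taking the earlier date. SAP 7.4 (on-treatment period) and 17.3 (on-treatment death flag) use the same cut-off. Drug-related SAEs after the cut-off still count as TEAEs.

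**The concern.** Progression is a usual reason for starting new therapy, so the two dates often lie close together. A rule that places the therapy as early as the day after last dose can put it before a progression that in fact led to it. The plan then treats an observed event as progression under another treatment and replaces it with an earlier censored time. That censoring is informative, because it falls on patients known to have progressed, and it pushes the Kaplan-Meier PFS estimate up.

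On the safety side, Protocol 6.2.5 has sites collect all AEs until 30 days after last dose or the actual start of new therapy. Where the imputed start is too early, AEs properly collected before the true start can drop out of the TEAE summaries. TEAEs are the primary endpoint of Stage 2, and the loss lowers their incidence.

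**Working it through.** **Inputs.** The five branches above (SAP 7.10); row 5 and the same-day rule (SAP 16.5); PFS = (date − first dose + 1)/30.4375 months (SAP 16.5); post-dose TEAE tail = min(30, new-therapy start − last dose) days (SAP 17.2). The plan gives no figure for the effect of this rule.

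**The SAP's own day arithmetic.** Table 2 footnote [a] reproduces: 2×(56+7) = 126; 2×56+7 = 119; 56+84+14 = 154; 2×(84+7) = 182.

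**Illustrative dates (assumptions, not trial data).** First dose is 1 July 2021.

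| Recorded part | Last dose | Imputed start | Documented PD | True start | Last evaluable scan before imputed start |
|---|---|---|---|---|---|
| March 2022 | 2 Mar 2022 | 3 Mar 2022 | 24 Mar 2022 | 30 Mar 2022 | 16 Dec 2021 |
| April 2022 | 2 Mar 2022 | 15 Apr 2022 | 20 Apr 2022 | 27 Apr 2022 | 16 Dec 2021 |
| 2022 | 2 Mar 2022 | 3 Mar 2022 | 10 May 2022 | 20 May 2022 | 20 Feb 2022 |
| 2022 | 20 Nov 2021 | 1 Jul 2022 | 1 Aug 2022 | 20 Aug 2022 | 5 May 2022 |
| nothing | 2 Mar 2022 | 3 Mar 2022 | 10 May 2022 | 20 May 2022 | 20 Feb 2022 |

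Results, in the same row order:

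| PFS as planned | PFS with the true start | Tail as planned | Tail with the true start |
|---|---|---|---|
| censored, 169/30.4375 = 5.55 | event, 267/30.4375 = 8.77 | 1 day | 28 days |
| censored, 169/30.4375 = 5.55 | event, 294/30.4375 = 9.66 | 30 days | 30 days |
| censored, 235/30.4375 = 7.72 | event, 314/30.4375 = 10.32 | 1 day | 30 days |
| censored, 309/30.4375 = 10.15 | event, 397/30.4375 = 13.04 | 30 days | 30 days |
| censored, 235/30.4375 = 7.72 | event, 314/30.4375 = 10.32 | 1 day | 30 days |

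The gaps from last evaluable scan to PD are 98, 125, 79, 88 and 79 days. All are below the 182-day limit that applies from Day 162, so the missed-visit rule would not have censored these patients. The imputed date alone does it.

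**What follows.**
- A PFS event can be lost in all five branches. The condition is always imputed start < PD ≤ true start. PD on or before the imputed start stays an event.
- In the same-month branch the start can be at most 29 days too early (last dose on the 1st of a 31-day month, true start on the 31st: 31 − 2 = 29). In the year-only and fully missing branches the error can be months.
- The tail falls to 1 day only in the three last-dose + 1 branches. With the 15th of the following month it is 15 to 30 days. With 1 July of a later year it is 30 days for a last dose before 2 December or so, as in the fourth row, and always for later ones.

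**Same cases under the fix.** With the efficacy date bounded by PD + 1, the imputed starts become 25 March, 21 April, 11 May, 2 August and 11 May, and all five cases return to events at 8.77, 9.66, 10.32, 13.04 and 10.32 months. With the latest compatible date for safety, the first case ends on 31 March (31 − 2 = 29 days) and the others keep 30 days.

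**The case against.** **Few patients are exposed.** Dosing normally continues to progression, and PD on or before the imputed start is safe. The risk falls on patients whose last dose came before documented PD: those who stopped for toxicity and were still scanned, or those scanned during a dose hold (SAP 15 takes the last non-zero dose, and the tables in Protocol 6.8 allow holds that resolve within 28 days). Amendment 5 ended post-treatment scans, so the first group comes mainly from earlier follow-up. This stands. It limits the size but does not remove the fault.

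**The consequence is visible and modest.** PFS is a secondary, descriptive endpoint in an open-label phase 1 trial, and censoring reasons are tabulated and listed by patient. All AEs are still listed, and the death flag affects only a listing. This also stands, but a row-5 label would not show that the therapy date had been imputed.

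**Not every effect favours the drug.** The window for best overall response (SAP 16.1) also closes at new therapy, so an early imputed date could exclude a late response. True, and the fix should cover it.

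**Stronger readings the documents do not support.**
- *The TEAE window shrinks to a day.* It opens at first dose. Only the part after last dose is cut, only in three branches, and drug-related SAEs are kept.
- *The SAP contradicts its own default.* SAP 17.2 says "In the case where it is not possible to classify an AE as treatment-emergent or not, the AE will be classified as treatment-emergent", but this follows a reference to partial AE dates. It may not extend to an uncertain therapy date; if it does, the AEs are retained. What is missing is a statement of which rule prevails.
- *DoR events are lost in the same way.* The censoring sentence in SAP 16.6 is worded for responders without PD or death. Loss of DoR events follows only if the whole PFS table is meant to apply.

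**Conclusion.** The point holds for PFS: applied as written, the rule can turn a documented progression into an earlier censored time, and the bias is upward. In the illustrative cases the recorded time moves back by 2.60 to 4.11 months (10.32 − 7.72 and 9.66 − 5.55), so the shift is not confined to one scan interval. For safety, the post-dose tail falls from 30 days to about 1 in three of five branches for AEs other than drug-related SAEs, unless the treatment-emergent default is meant to override the imputed date.

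These sizes are per affected patient and rest on assumed dates. A reader might want a multiplier on median PFS, but the documents give neither the number of incomplete therapy dates nor the number of affected events, so none can be supported. If no therapy date is incomplete, there is no effect. The correction is worth making before database lock because it is cheap and the SAP already applies such checks to other imputed dates.

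**What to change.** In SAP 7.10, under subsequent anti-cancer therapy:

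- **Efficacy.** For PFS, set the imputed start to the later of the current value and documented PD date + 1, whenever the recorded part of the date allows it. Use the same date to close the best-overall-response window. Apply it to DoR if the PFS table is meant to govern DoR, and reword SAP 16.6 to say whether it does.
- **Safety.** For the TEAE, on-treatment and on-treatment-death cut-offs, use the latest date compatible with the recorded part. If the date is fully missing, do not shorten the 30-day window. State in SAP 17.2 whether the treatment-emergent default overrides an imputed therapy date.

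The cost is SAP wording and one derivation, with no new data. There are two small downsides. A few PDs or AEs that truly followed new therapy may be counted: part one resolves doubt in favour of an event, and in the first worked case the safety tail is 29 days against a true 28. Efficacy and safety derivations may also carry different imputed dates for the same patient, which the analysis datasets should flag.

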6. Patients with presence of second primary malignant tumors within the last 2 years, with the exception of:
- Basal cell carcinoma of the skin
 - Squamous cell carcinoma of the skin
 - Carcinoma in situ of the cervix
 - Carcinoma in situ of the breast
7. Clinically significant history of liver disease, including cirrhosis, current alcohol abuse, or current known active infection with human immunodeficiency virus (HIV), hepatitis B virus (HBV), hepatitis C virus (HCV), or cytomegalovirus (CMV); Active infection is defined as one requiring treatment with antiviral therapy, presence of positive test results for hepatitis B (hepatitis B surface antigen and/or total hepatitis B core antibody), or CMV or HCV antibody
- Patients who are positive for hepatitis B core antibody are eligible only if test results are also positive for hepatitis B surface antibody and polymerase chain reaction (PCR) is negative for HBV deoxyribonucleic acid (DNA). These patients will require HBV DNA PCR monitoring, as per local standards
 - Patients who are positive for CMV or HCV serology are eligible only if testing for CMV DNA or HCV RNA is negative.
8. Any anticancer therapy, including chemotherapy, hormonal therapy, biologic therapy, vaccine, or radiotherapy within 3 weeks prior to initiation of study treatment;
9. Any granulocyte colony-stimulating factor treatment/blood transfusion within 7 days before the screening hematology test;

10. Any steroid therapy or approved targeted small molecule agents for anti-neoplastic intent within 7 days or approximately 5 half-lives, whichever is longer, prior to initiation of study treatment;
11. Prior use of any drug that is a strong inducer of CYP3A4 or strong inhibitor of CYP3A4 within 2 weeks prior to initiation of study treatment (3 weeks for St John's Wort) (refer to [Appendix 8](#));
12. Prior autologous transplant within 6 months prior to initiation of study treatment;
13. Prior allogeneic stem cell transplant within 6 months prior to initiation of study treatment or with any evidence of active graft versus host disease or requirement for immunosuppressants within 21 days prior to initiation of study treatment;
14. Clinically significant active infection (e.g., pneumonia) or interstitial lung diseases (including drug induced pneumonitis);
15. Major surgical procedure within 4 weeks prior to initiation of study treatment;

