- If both the day and month are missing or a date is complete missing, it will be considered as missing.

Prior oncology anti-cancer Medications

Missing or partial start dates:

- If the date has no missing year and month but the day is missing, 1st day of the month will be used.
- If the date has no missing year, but has missing month, then January 1st will be used.
- If the start date is completely unknown, do not impute the start date.

Missing or partial stop dates:

- If the date has no missing year and month but the day is missing, then use the last day of the month.
- If the date has no missing year, but has missing month, then use December 31st of that year.
- If the stop date is completely unknown, do not impute the stop date, and assign 'ongoing' status.

Note: If the imputed stop date is earlier than the start date, then the stop date is imputed with the start date. For patients who died, if the imputed start/stop date is later than date of death, the imputed date will set to be date of death. If the imputed stop date is after the last known alive date, then the stop date is imputed with the last known alive date.

Efficacy Analyses Data

Missing efficacy response will be treated as Not Evaluable (NE) at the visit.

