12. PRIOR ONCOLOGY THERAPY

Prior oncology therapy will be summarized for the FAS. Prior oncology therapies are defined as any anti-cancer therapy taken prior to initiation of study treatment. Prior oncology therapies include prior oncology chemotherapy and oncology medication, prior oncology radiotherapies and prior oncology surgeries/procedures.

Prior oncology surgeries/procedure

Prior oncology surgeries/procedures will be coded using MedDRA Version 26.0 or higher (depends on the latest data coding). Number and percentage of patients taken prior oncology surgeries / procedure will be summarized.

All prior oncology surgeries / procedure records will be listed with system organ class (SOC) and PT in the listing.

Prior oncology radiotherapy

Radiotherapies are not considered a line of prior oncology therapy. Radiotherapies will be summarized by numbers and percentages of patients taken radiotherapies, and all radiotherapy records will be listed.

Prior oncology chemotherapy and oncology medication

Prior oncology medication therapies will also be summarized as follows:

- Number and percentage of patients with at least one prior oncology medication therapy
- Number of previous lines of therapy
- Number and percentage of patients with 1, 2, 3, and >3 previous lines of therapy
- Time since last oncology medication therapy (month) = (date of first dose last date for the last therapy + 1)/30.4375
- Number and percentage of patients with Progression of Disease within 24 months

Protocol Number: 2018-689-00US1 Page 27 of 43

from the start of the first line of prior therapy (yes/no).

- Number and percentage of patients with any prior CD20 medication therapy
- Number and percentage of patients with any prior BTK inhibitor medication therapy

Prior oncology medications will be coded using World Health Organisation Drug Dictionary Enhanced (WHO-DDE) version MAR2023 or higher.

All prior oncology chemotherapy and oncology medication records will be listed with ATC level 2 text and preferred term (PT) in the listing.

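### Partial stop dates of prior anti-cancer drugs are imputed late with no bound at first dose, so time since last oncology medication can come out negative

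*SAP*

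**What the plan says.** SAP 7.10, under prior oncology anti-cancer medications, has three rules for stop dates:

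- Day missing: "If the date has no missing year and month but the day is missing, then use the last day of the month".
- Month missing: "If the date has no missing year, but has missing month, then use December 31st of that year".
- Everything missing: "If the stop date is completely unknown, do not impute the stop date, and assign" a status of 'ongoing'.

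The closing note bounds the result in three ways. From below: "If the imputed stop date is earlier than the start date, then the stop date is imputed with the start date". From above, by death: "For patients who died, if the imputed start/stop date is later than date of death, the imputed date will set to be date of death". Also from above, by the last known alive date. First dose is not mentioned.

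SAP 12 states the scope of this class: "Prior oncology therapies are defined as any anti-cancer therapy taken prior to initiation of study treatment". It then tabulates time since last oncology medication, in months, as first dose minus the last date of the last therapy, plus 1, divided by 30.4375. (The minus sign is lost in the extracted text and is read as subtraction here.) SAP 7.1 says that durations resting on partial or missing dates use the imputations of 7.10.

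Protocol 5.1.2, exclusion 8, excludes patients with "Any anticancer therapy, including chemotherapy, hormonal therapy, biologic therapy, vaccine, or radiotherapy within 3 weeks prior to initiation of study treatment". Exclusion 10 sets a shorter window, 7 days or about 5 half-lives if longer, for anti-neoplastic steroids and approved targeted small molecules.

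**The concern.** In an eligible patient, every prior anti-cancer drug covered by these exclusions stopped before first dose. The imputation does not use that knowledge. It takes the latest date compatible with the recorded fragment, which can lie after first dose. The two upper limits do not help: in a treated patient, neither death nor the last known alive date can precede first dose.

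Other rules in SAP 7.10 do tie such dates to a study milestone. Imputed diagnosis dates are capped at informed consent, and an unknown start of subsequent anti-cancer therapy is set to the day after last dose. Prior anti-cancer medication has no comparable anchor.

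At stake is the credibility of one baseline row. A negative time since the last prior therapy is impossible. It would set the reported minimum and pull the mean in what may be small groups, since Stage 1 is tabulated by dose level and Stage 2 by malignancy. SAP 7.10 keeps imputed dates out of the listings, so a reader of the tables could not trace the value to its cause.

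**Working it through.** The plan gives no figure on this point, so there is none to reproduce. The check applies the SAP 7.10 rules and the SAP 12 formula to example dates. All calendar dates and true gaps below are assumptions. The patient is assumed to be known alive beyond the imputed date, so the upper limits do not act.

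Formula: T = (first dose - stop date + 1)/30.4375, with dates in days. Because of the +1, T is negative once the stop date is at least 2 days after first dose.

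**Month missing.** Recorded stop '2021', first dose 15 June 2021.
- Imputed stop 31 December 2021: T = (-199 + 1)/30.4375 = -198/30.4375 = -6.5 months.
- If the true stop was 1 March 2021: T = (106 + 1)/30.4375 = 107/30.4375 = +3.5 months.
- Error: (-198 - 107)/30.4375 = -10.0 months. In a dose level of 3 patients, the plan's minimum cohort size, this one value moves the mean by -10.0/3 = -3.3 months.

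**Day missing.** Recorded stop 'March 2021', first dose 25 March 2021.
- Imputed stop 31 March: T = (-6 + 1)/30.4375 = -0.16 months.
- If the true stop was 3 March, 22 days before first dose and so outside the 3 weeks: T = (22 + 1)/30.4375 = +0.76 months.

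**Stop date fully unknown.** Nothing is imputed, so T is missing, not negative. The therapy is labelled 'ongoing'.

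**How often a partial date gives a negative T.** Take every 2021 date as first dose and fix the true gap from last therapy at g days.
- Month missing: the stop must fall in 2021 and first dose on or before 29 December (day 363), so the share is (363 - g)/365.
- Day missing, stop on day s of a month with L days: negative if s + g is at most L - 2. For g = 22 that is L - 24 days a month: (7 x 7 + 4 x 6 + 1 x 4)/365 = 77/365 = 21.1%.

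| True gap (days) | Day missing: T negative | Month missing: T negative | Month missing: lowest T (months) |
|---|---|---|---|
| 22 | 21.1% | 93.4% | -11.20 |
| 28 | 1.9% | 91.8% | -11.01 |
| 60 | 0% | 83.0% | -9.95 |
| 90 | 0% | 74.8% | -8.97 |
| 180 | 0% | 50.1% | -6.01 |

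These are shares among records already partial in the stated way, not shares of patients. With only the day missing, T cannot be negative for gaps above 31 - 1 - 2 = 28 days. The 31 December rule is the main source.

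**Effect of a cap.** A stop date set to the day before first dose gives T = (1 + 1)/30.4375 = 0.07 months. Date order is restored, but the value still lies inside the 3-week window; 22 days before first dose would give 0.76 months.

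**The case against.** The strongest reply is that this is a tidy-up. The variable is one descriptive line in an uncontrolled phase 1 study; no endpoint, analysis set or censoring rule uses it, and SAP 7.6 plans no subgroups. The -6.5-month example also needs the last therapy to have a year-only stop date in the year of first dose, although eligibility had to be confirmed before dosing (Protocol 5.7.2 and 5.7.14.1). In the more plausible day-missing case, negatives are small and confined to short gaps. All of this stands and limits the size of the point. It does not make the stated rule right.

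A reader might infer more, but the documents do not support it:

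- *That this row is the only tabulated check on the washout.* SAP 9.2 tabulates major protocol deviations by category and lists all deviations, and SAP 9.1 lists eligibility against the entry criteria. The SAP does not present this row as a washout check.
- *That compliant patients would be reported as washout violators.* Deviations are collected by the clinical team in the trial management system, not derived from SAP 12, and imputed dates stay out of listings. At most, an odd value appears in the summary statistics.
- *That the 'ongoing' rule produces negative durations.* It leaves the duration missing; only the label is wrong.
- *That the wrong therapy would be picked as the last one.* That assumes selection by imputed stop date. SAP 12 states no selection rule.

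**Conclusion.** The point holds, and it is minor. As written, SAP 7.10 can place the stop of a prior anti-cancer drug after first dose, and the SAP 12 formula then returns an impossible negative value: -6.5 and -0.16 months in the two examples, and as low as -11.20 months with a year-only date and a true gap of 22 days. Separately, labelling an unknown stop date 'ongoing' contradicts the SAP's definition of prior therapy, without affecting the duration.

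The effect is confined to one descriptive baseline variable and the derived dates behind it. The sizes rest on assumed dates and on the patient being known alive past the imputed date; an earlier last known alive date shrinks the error but does not bring the stop date before first dose. How many patients have partial stop dates is not given, so the effect on the actual table cannot be estimated and may be nil.

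**What to change.** In SAP 7.10, for prior anti-cancer medications only:

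1. Set any imputed stop date on or after first dose to the day before first dose, and flag it.
2. Leave time since last oncology medication missing when only the year is known and it is the year of first dose.
3. Leave a completely unknown stop date missing, without assigning 'ongoing'.

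Step 1 alone is not enough, because it would turn the year-only example into 0.07 months, which is plausible in sign but uninformative; step 2 removes it.

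The cost is a few sentences, a small programming change, and a few more missing or flagged values in one baseline row. A footnote should say that a capped date is the latest the stop could have been, so the capped duration is a minimum and does not measure washout compliance.
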